The data will be presented with descriptive statistics, mean and standard or median deviation and interquartile travel, as well as percentages and incidence. For comparisons of numeric variables between study groups, we will use Student t if the distribution of the data follows a normality pattern, otherwise the Mann-whitney U test will be used; to compare qualitative variables we'll use square Chi. Analysis by intent to be treated and analyzed by protocol shall be performed and considered as significant when the p-value is <0.05. For the analysis and presentation of the data we will use the sPSS Version 15 and GraphPad Prism program 5.

ETHICAL ASPECTS

Ethical standards, Regulations of the General Health Law on Health Research and the Helsinki Declaration of the World Medical Association of the 64th General Assembly, StrongHold, Brazil in 2013 and current international codes and standards of good clinical research practices. Special attention will be given to taking care of the privacy and

autonomy of the patient. Once the patient has been informed about the study and agrees to participate in it, and since it involves a greater risk to a minimum, the signature of informed consent letter will be requested.

BIBLIOGRAPHIC REFERENCES:

4. Villalpando S, de la Cruz V, Rojas R, Shamah-Levy T, Avila MA, Gaona B, et al. Prevalence and distribution of type 2 diabetes mellitus in Mexican adult population: a probabilistic survey. *Salud Publica Mex* [Internet]. 2010 [cited 2018 Apr 7];52 Suppl 1:S19-26. Available from: <http://www.ncbi.nlm.nih.gov/pubmed/20585724>

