Type of Study: Clinical trial (randomized, controlled and triple-blind).

MATERIAL AND METHODS.

Study universe: Mexican patients with prediabetes and overweight/obesity.

Study population: Mexican patients with prediabetes and overweight/obesity, from the State of Guanajuato.

Place of realization: Hospital Metabolism Laboratory of Division of Health Sciences of the University of Guanajuato, León, Gto.

Type of sampling: Non-probabilistic, of consecutive cases.

Sample size: The calculation of the sample size was based on the formula for comparing proportions. We hope that the low-dose combination of linagliptin + metformin will improve the outcome variables (insulin resistance, pancreatic beta cell function and cardiovascular function) by at least 75%, metformin use alone achieves this only by 30%(44.46), so the study is designed to detect a minimum difference of 45% between study groups with a type I (alpha) error of 0.05 and a sample power of 80% , and according to the following formula(70):

$$n = \frac{(Z\alpha/2 + Z\beta)^2 p^- (1-p^-)(r + 1)}{(d)^2 r}$$

Where,

$$(Z\alpha/2 + Z\beta)^2 = 7.9$$

p^1 = proportion of individuals in the best treatment who failed to achieve improvement = 0.25

p^2 = proportion of individuals in the worst treatment who failed to achieve improvement = 0.70

r = reason for individuals in treatment groups = 1

d = difference you're expected to find = 0.45

n = 14 + 20% of losses = 17 patients per group

SELECTION CRITERIA TO PARTICIPATE

- Women and men aged 18 to 65 overweight or obese (BMI 25 kg/m²)
- Patients with prediabetes, defined by:
 - 1) Glucose intolerance (ITG = glucose at 2h en la CTOG between 140-199mg/dL).

2) The coexistence of fasting impaired glucose (GAA = fasting glucose between 100 and 125mg/dl) and glucose intolerance (ITG = glucose at 2h in CTOG between 140-199mg/dL).

- Those who agree to participate in the study sign an informed consent letter.

NOT SELECTED TO PARTICIPATE

- Patients with DM2 previously diagnosed or detected during sampling and CTOG.
- People currently being treated or for the past 3 months with metformin, pioglitazone, or any other antidiabetic drug, including insulin.
- Serum creatinine >1.6mg/dl.
- Very high hipertriglyceridemia (>500mg/dl).
- Pregnant women.
- Uncontrolled arterial hypertension (systólic >180mmhg o diastolic >105mmHg).
- Excessive alcohol intake, acute or chronic.

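### The stated 80% power comes from a two-proportion calculation on an undefined responder outcome, so it is not established for the t or Mann-Whitney comparisons that test the hypothesis

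*Combined protocol and SAP*

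**What the plan says.** The Sample size paragraph (Material and Methods) states that "The calculation of the sample size was based on the formula for comparing proportions". It expects the combination to "improve the outcome variables (insulin resistance, pancreatic beta cell function and cardiovascular function) by at least 75"%, while "metformin use alone achieves this only by 30"%, and sets the design "with a type I (alpha) error of 0.05 and a sample power of 80"%. The two inputs to the formula are "proportion of individuals in the best treatment who failed to achieve improvement = 0.25" and "proportion of individuals in the worst treatment who failed to achieve improvement = 0.70". The result is 14 per group, raised to 17 for 20% losses.

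The three outcomes named there are the three in the Hypothesis section. The table of variables defines each as quantitative:

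- beta-cell function: the ratio of the 0-30 minute insulin and glucose increments;
- insulin sensitivity: the Matsuda index;
- cardiovascular function: echocardiographic measures, including ejection fraction.

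The Statistic Analysis section says of numeric variables that "we will use Student t if the distribution of the data follows a normality pattern", with Mann-Whitney U otherwise. Chi-square is reserved for qualitative variables.

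**The concern.** The calculation treats each patient as improved or not improved. Nothing in the plan says what improvement means for the Matsuda index, the beta-cell index or ejection fraction, and no responder analysis of them is planned. The sample-size wording is itself ambiguous: an improvement of at least 75% can be read as a size of change, whereas the formula uses it as a share of patients (1 - 0.75 = 0.25 failing).

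The test that was powered is therefore not run on these outcomes, and the tests that will be run were not powered. What is at stake is how a null result would be read. The question is whether adding linagliptin to metformin helps, and a non-significant comparison could be taken as evidence of no added effect from a trial with 80% power, when that figure belongs to a different analysis.

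**Working it through.** **Inputs from the plan.** Failure proportions 0.25 and 0.70; d = 0.45; r = 1; squared sum of normal quantiles 7.9, with the two-sided Z for alpha/2; 14 per group, then 17. No mean difference or SD is given for any hypothesis outcome. The standardized differences in steps 3 and 4 are therefore assumptions.

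**1. The plan's own figure.** The printed formula is n = 7.9 × p̄(1 - p̄)(r + 1) / (d² r). Taking p̄ as the mean of the two proportions, (0.25 + 0.70)/2 = 0.475:

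n = 7.9 × 0.475 × 0.525 × 2 / 0.45² = 3.940 / 0.2025 = 19.46, so 20 per group.

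The stated 14 is not reproduced. This arithmetic fault is separate from the mismatch of scale, but it limits the remedies. Power of the chi-square test for 0.25 versus 0.70, by exact enumeration (two-sided 0.05), is 66% at 14 per group, 80% at 17 and 82% at 20.

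**2. Which analysis the 80% could belong to.**

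| Outcome | Scale in variables table | Responder cut-off | Planned test | In hypothesis | In sample-size paragraph |
|---|---|---|---|---|---|
| Beta-cell function | Quantitative | None | t or Mann-Whitney | Yes | Yes |
| Insulin sensitivity / resistance | Quantitative | None | t or Mann-Whitney | Yes | Yes |
| Cardiovascular function | Quantitative | None | t or Mann-Whitney | Yes | Yes |
| Glucose homeostasis | Yes/No | 2-hour glucose 140 mg/dL | Chi-square | No | No |

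No row combines a proportion-based test with a place in the sample-size paragraph.

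**3. Detectable difference on the analysis scale.** For a two-sample t test, two-sided 0.05, power comes from the noncentral t distribution with 2n - 2 degrees of freedom and noncentrality δ√(n/2), where δ is the difference in SD units. Solving for 80% power:

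- n = 14 evaluable per arm: δ = 1.10
- n = 17 evaluable per arm: δ = 0.99

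For Mann-Whitney, using relative efficiency 0.955 under normality (effective n = 0.955 × n), the values are about 1.13 and 1.02. The 17-per-arm figures require every enrolled patient to be evaluable. With the planned 20% losses, 17 × 0.8 = 13.6, so the 14-per-arm figures apply.

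**4. t-test power over an assumed range.**

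| Assumed difference | 14 evaluable per arm | 17 evaluable per arm | Evaluable per arm for 80% |
|---|---|---|---|
| 0.5 SD | 25% | 29% | 64 |
| 0.8 SD | 53% | 62% | 26 |
| 1.0 SD | 72% | 81% | 17 |
| 1.2 SD | 86% | 92% | 12 |

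**5. What the plan's proportions would imply if a cut-off existed.** Suppose 0.25 and 0.70 failing came from cutting a normal variable with equal SDs in the two arms. The implied shift is z(0.70) - z(0.25) = 0.524 + 0.674 = 1.20 SD. t-test power is then 86% at 14 per arm and 92% at 17.

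**The case against.** The strongest reply is step 5: a t test uses more information than a dichotomy. If the proportions reflect a cut normal variable, the continuous analyses exceed 80% even at 14 per arm. This stands, and it rules out the stronger reading that a reader might infer, namely that the hypothesis tests are shown to have less than 80% power. The documents do not support that reading, because they give no mean difference or SD. Equally, they do not state the 1.20 SD shift, a cut-off or a distribution, so the reply does not establish the 80% either. It would also need an effect of that size on every named outcome, ejection fraction included.

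A second reply is that the paragraph openly targets a 45-point difference, so a reader knows that only a large effect was sought. That softens the risk of misreading. It does not supply a power for the planned tests, and a difference in proportions without a cut-off cannot be turned into a difference in the Matsuda index.

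A third reply is that a binary outcome with a chi-square test does exist. It does: glucose homeostasis. But the plan ties neither 0.25 nor 0.70 to it, and it appears in neither the hypothesis nor the sample-size paragraph.

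Finally, 0.5 and 0.8 SD are not targets in the plan. They serve here only as an illustrative range.

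**Conclusion.** The point holds in this form: the 80% power is stated for an undefined responder proportion and is not established for the t or Mann-Whitney comparisons of the three hypothesis outcomes. On the analysis scale, the planned size gives 80% power for about 1.10 SD with 14 evaluable per arm, or about 0.99 SD if all 17 are evaluable (Mann-Whitney about 1.13 and 1.02). These figures assume a two-sided 5% level, equal arms, equal SDs and normality. Whether they are adequate cannot be judged from the documents, which give no target difference or SD for any of these outcomes.

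**What to change.** In the Sample size paragraph, drop the 80% claim for the three continuous outcomes and restate it on the analysis scale. Suggested wording: *At a two-sided 0.05 level, 14 evaluable patients per arm (17 enrolled, less planned losses) give 80% power for a difference of about 1.10 SD by t test (about 1.13 SD by Mann-Whitney); if all 17 are evaluable, about 0.99 SD (1.02 SD). Power at 14 / 17 evaluable is 25% / 29% for 0.5 SD, 53% / 62% for 0.8 SD and 72% / 81% for 1.0 SD; these differences are an assumed range.*

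Do not move the existing proportion calculation to glucose homeostasis as it stands, because that would carry over an 80% that the printed formula does not give at 14 per arm. If the sponsor wants that route, it must justify 0.25 and 0.70 for that outcome and correct the figure to 20 evaluable per arm.

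The restatement is a change of wording. Its cost is a less favourable stated power. It needs no extra patients and no change to conduct or analysis.

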One of the investigations that best show the impact of lifestyle modifications and the use of metformin on the prevention of DM2, is the Diabetes Prevention Program (DPP); This study was a randomized clinical trial with an average follow-up of 2.8 years, which included 3,234 patients with BMI > 24 and GAA and/or ITG that were randomized in 3 study groups: 1) Metformin 850mg daily treated during the first month and then 850mg twice a daily plus routine recommendations (orally and written) annually on lifestyle, 2) placebo treated group plus routine lifestyle recommendations, and 3) group treated with an intensive lifestyle modification program, which consisted of performing 150min of physical activity per week and reducing fat intake and calories in the diet, in order to lose 7% of

body weight. This group had 16 personalized sessions during the first 24 weeks, and then every month. It is worth mentioning that in this study, only 50% of the participants in the intervention group to modify the lifestyle managed to lose 7% of body weight within 24 weeks of initiation, and only 38% maintained it until the end of the study; 74% maintained the required physical activity 24 weeks after the study and only 58% until the end of the study; at 24 weeks of the study, the intervention group achieved a reduction in energy intake of 450 kcal/day compared to approximately 250 kcal/day in the other two groups. The results showed that with intensive changes in lifestyle, the risk of DM2 was reduced by 58%, and with metformin by 31%; even so, the cumulative incidence of DM2 in 3 years was 14.4% in the intervention group, 21.7% in the metformin group, and 28.9% in the placebo group(44). However, the long-term results (15 years) of this type of interventions have shown that the effect is lost over time and that eventually most patients will develop DM2.

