Other antidiabetic medications that have been used are: acarbose, which in a cohort of 1429 patients with ITG showed a reduction in the risk of DM2 of 25% with a necessary number to treat of 11 to avoid a case of DM2, however, more than a quarter of patients did not complete the follow-up due to side effects of the medication(45); rosiglitazone in the DREAM study that included 5269 patients with GAA and/or ITG randomized 4-8mg of rosiglitazone or placebo, at an average follow-up of 3 years, the rosiglitazone-treated group showed a DM2 risk reduction of 62%(46); The ACT NOW study that used pioglitazone 45mg a day in subjects with GAA and/or ITG shows a risk reduction of DM2 of about 80% compared to placebo(47).

Currently, the pharmacological interventions used in patients with DM2, are directed towards the pathophysiological alterations, while in prediabetes, if we try to avoid the progression of the disease, it is clear that the options that can greatly impact each of the pathophysiological alterations are those that could have greater effect to prevent disease progression(28,29); within these pharmacological interventions, those that could be more effective, due to the pharmacological profile, are:

- 1) **METFORMIN:** Metformin is the most widely used antidiabetic drug in the world. Although its main effect is exerted at the liver level, it also has an effect on the tissue such as muscle, adipose and endothelial tissue; most of its effects are related to the control of insulin resistance and/or hyperinsulinemia. At the liver level, metformin activates an enzyme known as AMP kinase (AMPK), which causes an inhibition of lipogenic and gluconeogenesis enzymes, decreasing lipolysis, increasing fatty acid oxidation, reducing hepatic glucose production (gluconeogenesis), increasing hepatic glucose uptake and glycolysis, all this is because increases the sensitivity to the effect of insulin. At the muscle level, metformin also works by improving muscle glucose uptake, among other effects. It is the only medication approved for use in people with prediabetes; it is associated with weight reduction in a variable percentage, as monotherapy is very unlikely to cause hypoglycemia. The disadvantage of metformin is that it has been observed in long-term studies in prediabetes (15 years of follow-up) that the effect is almost equated to a placebo and that eventually the majority of treated patients will develop DM2.

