in insulin secretion, alpha cell dysfunction with increased glucagon production, and amyloid deposits) and this is a crucial event for the progression of prediabetes disease to DM2, so medications that can improve the functionality of this islet, increasing insulin secretion and reducing glucagon, could have a major impact on the disease. There are two incretins, GLP-1 and GIP, of these two, the first being found reduced in patients with DM2 and with prediabetes(33,34,49,50) and both are produced and released by intestinal cells. The pharmacological effects of incretins are: increased insulin secretion, decreased glucagon secretion, delay gastric emptying, and reduced appetite leading to weight reduction. In general there are two ways to increase the incretin effect, by applying incretin analogues, which are injectable, and by inhibiting the enzyme that degrades to endogenous GLP-1, which is dipeptidyl-peptidase 4. As the incretin effect is reduced in patients with DM2 and with prediabetes, and knowing that the effect of incretinomimetic medicinal products improves pancreatic islet function and could have some effect on the peripheral action of insulin(51–54), it is interesting to know the impact they could have on DM2 prevention, especially when combined with insulin sensitizers. There are few studies that evaluate the effect of incretins on people with prediabetes; with GLP-1 analogues, one study randomized 38 patients with GAA or ITG to receive exenatid 10 g every 12 hrs subcutaneously for 24 weeks, finding that in addition to the weight-reducing effect, a large percentage of patients with prediabetes treated with exenatide reverted to normal (77% vs. 56% for the placebo group)(55). Another randomized clinical trial compared the effect of liraglutide, another LPG-1 analogue, on glucose metabolism, insulin resistance and insulin secretion in 24 patients treated with liraglutide and 27 with placebo, of which 10 and 11, respectively, they had altered fasting glucose + glucose intolerance; achieved a 29% reduction in peripheral insulin resistance and a 21% increase in insulin secretion(56). In another study, 22 patients with GAA were randomized to receive 100 mg of sitagliptin, DPP-IV inhibitor, for 8 weeks reporting no effect on glucose metabolism, although reports of some clinical cases mention important effect glucose in patients with prediabetes.

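### The 30% metformin improvement rate is not supported by the two references cited for it, and the stated 80% power is not reached at 14 evaluable patients per group even if 30% is accepted

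*Combined protocol and SAP*

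**What the plan says.** The Sample size paragraph (Material and Methods) uses a formula for comparing two proportions. The expected improvement is 75% on linagliptin plus metformin, introduced as a hope and without a citation. For the comparator, "metformin use alone achieves this only by 30%(44.46"). The formula inputs restate these as failures: "p^1 = proportion of individuals in the best treatment who failed to achieve improvement = 0.25" and "p^2 = proportion of individuals in the worst treatment who failed to achieve improvement = 0.70", with "d = difference you're expected to find = 0.45". The target is a "type I (alpha) error of 0.05 and a sample power of 80"%. The result is 14 per group, raised to 17 for 20% losses.

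The Treatment of Prediabetes section summarises the two cited sources. For reference 44, the diabetes prevention trial with an average follow-up of 2.8 years, "the risk of DM2 was reduced by 58%, and with metformin by 31"%; cumulative three-year incidence was 21.7% on metformin and 28.9% on placebo. For reference 46, which compared rosiglitazone with placebo, "the rosiglitazone-treated group showed a DM2 risk reduction of 62%(46").

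The only proportions in the protocol for return to normal glucose status come from a 24-week exenatide study, described under Incretines: "77% vs. 56% for the placebo group".

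**The concern.** The formula needs a responder proportion: how many metformin patients out of 100 improve by 6 months on the outcomes named. The references attached to the 30% are described as reporting something else, namely relative reductions in new diabetes over about three years, and one of them concerns a different drug. A relative risk reduction cannot be read as a responder proportion.

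The control rate fixes the 45-point difference, and with it the sample size and the power claim. A reader who sees 80% power backed by two citations may take a null result as evidence that linagliptin adds nothing. With 14 to 17 patients per group, that reading is safe only if the inputs are sound and the arithmetic is right.

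**Working it through.** **1. The plan's own figure.** Inputs from the Sample size paragraph: failure proportions 0.25 and 0.70, d = 0.45, r = 1, multiplier 7.9. The mean failure proportion is (0.25 + 0.70)/2 = 0.475.

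Printed formula: n = 7.9 × 0.475 × 0.525 × 2 / 0.45² = 3.940 / 0.2025 = 19.46, so 20 per group. The stated 14 is not reproduced. Other two-sided forms give 19 (Fleiss), 23 (with continuity correction), 17.95 (arcsine) and 15.4 (unpooled variance). One-sided forms come nearer to 14 (Fleiss 15, arcsine 14.1, unpooled 12.1), but the plan prints a two-sided multiplier.

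The losses step does reproduce: 14 × 1.2 = 16.8, so 17. With 20% lost from 17, about 14 remain (17 × 0.8 = 13.6).

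**2. Power on the plan's own rates.** The Statistic Analysis section names chi-square for qualitative variables, with p < 0.05. Enumerating every outcome for 75% versus 30% with the uncorrected test gives 66.0% power at 14 per group and 79.9% at 17. The normal approximation gives 68% and 77%. With Yates' correction or Fisher's test, power is about 52% and 68%. The stated 80% is thus approached only if all 17 randomised per group contribute an outcome and the uncorrected test is used.

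**3. The source of the 30%.** Set side by side:
- *Needed:* the proportion of metformin patients improving in insulin resistance, beta-cell function or cardiovascular function at 6 months.
- *Reference 44 as described:* 31% relative reduction in diabetes risk over an average of 2.8 years.
- *Reference 46 as described:* 62% reduction in diabetes risk, rosiglitazone against placebo; no metformin arm is mentioned.

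Neither description contains the needed quantity.

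**4. Sensitivity to the rates (hypothetical).** Exact power, uncorrected chi-square, two-sided 0.05:

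| Combination v metformin | Difference (points) | 14 per group | 17 per group |
|---|---|---|---|
| 75% v 30% (plan) | 45 | 66% | 80% |
| 85% v 40% | 45 | 72% | 81% |
| 75% v 40% | 35 | 45% | 58% |
| 75% v 50% | 25 | 27% | 33% |
| 75% v 56% | 19 | 18% | 21% |
| 77% v 56% (exenatide v placebo, illustration only) | 21 | 22% | 25% |

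In the three rows with the combination held at 75% and metformin at 40%, 50% or 56%, the effect shrinks as the control rate rises. That shrinkage is what lowers the power: the 85% v 40% row keeps the 45-point difference and loses none.

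**The case against.** Several points on the other side stand.

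- A reader might infer that the 30% simply *is* the 31% risk reduction. That is probable, because no other metformin figure near 30% is reported from reference 44. But the plan never says how 30% was derived. Only the protocol's summaries of the references are available here, so the papers themselves may contain something relevant.
- A reader might infer from the exenatide row that this trial really has 20–25% power. The documents do not support that. The 77% and 56% come from another drug against placebo and concern return to normal glucose status, which is not among the three outcomes named in the sample-size calculation. The study randomised 38 patients, and no arm sizes are given. If about 18 were on placebo (an assumption), the exact 95% interval around 56% runs from about 31% to 78%, which barely excludes 30%.
- Both arms receive metformin 1700 mg daily, so a better metformin response could raise both rates.
- A reader might also infer that the trial is very likely to miss a real effect. The three outcomes named are classed as quantitative in the variables table and would be compared by t or Mann-Whitney. Chi-square responder power does not describe those tests, and their power cannot be calculated because no standard deviation is given.
- The protocol's report of no effect from a DPP-IV inhibitor concerns 8 weeks of sitagliptin in 22 patients with impaired fasting glucose. The same sentence mentions case reports of an important effect. It bears on the combination rate and does not settle the control rate.
- The plan openly presents 75% as a hope and 45 points as the minimum detectable difference, so part of the optimism is visible.

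None of this supplies a source for the 30% or brings the formula result to 14.

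**Conclusion.** The point holds in two parts. First, the 30% metformin rate lacks the support claimed for it: as the protocol describes references 44 and 46, neither gives a metformin responder proportion on the outcomes named. Second, the 80% power is not delivered at the 14 evaluable patients per group that the plan calculates, even if 75% versus 30% is accepted. The printed formula requires 20, and exact power is about 66% at 14 and 80% at 17.

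These figures assume a two-sided 5% uncorrected chi-square test on a responder outcome. The plan defines no improvement threshold for any of the three outcomes. How far power falls at other control rates depends on what is assumed for the combination arm, so the sensitivity rows illustrate the fragility and do not estimate the trial's true power.

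**What to change.** In the Sample size paragraph:

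1. Show how 30% was derived. Failing that, label it an assumption and remove the attribution to references 44 and 46.
2. Correct the formula result from 14 to 20 per group before losses. State the achieved power for 75% versus 30% as 66% with 14 and 80% with 17 per group, naming the test used.
3. Add the sensitivity table above, marked as hypothetical. Say that the rows with the combination held at 75% shrink the effect, that 85% v 40% keeps the 45-point difference, and that 77% v 56% is only an illustration from a different drug against placebo.
4. State that all these figures apply to a chi-square comparison of responders. They do not apply to the t or Mann-Whitney comparisons of the quantitative outcomes, for which the plan gives no standard deviation.

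This is rewording plus one small table. It needs no extra patients and no change to procedures. The cost is a less favourable stated power.

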- Medications or medical conditions affecting glucose homeostasis (thiazides, beta blockers, systemic glucocorticoids, weight-reducing or anorexigenic drugs, Cushing syndrome, thyrotoxicosis)

ELIMINATION

- Intolerance to the medicine used.
- Absence to more than 20 % of follow-up appointments.
- That they do not finalize the study and monitoring protocol.

VARIABLES

INDEPENDENT VARIABLES

- 1) *Intervention*

DEPENDENT VARIABLES

- 1) *Glucose homeostasis.*
- 2) *Sensitivity to insulin.*
- 3) *Pancreatic beta cell function.*
- 4) *Cardiovascular function.*

OPERATION OF VARIABLES, MEASUREMENT SCALES AND MEASUREMENT UNITS.

DEPENDENT VARIABLE	CONCEPTUAL DEFINITION	OPERATIONAL DEFINITION	CLASIFICATION	MEASURE- MENT LEVEL	INDICATOR
INTERVENTION	It is the established therapeutic strategy to prevent the progression of Prediabetes to type 2 diabetes mellitus and its complications.	
A. Administration of 1 tablet of linagliptin 2.5 mg /metformin 850 mg every 24 hours + 1 tablet of metformin 850 mg every 24 hours.
 
B. Administration of 1 tablet of metformin 850 mg every 12 hours.
	Qualitative	Nominal	
A. Group with low dose treatment of Linagliptin/ Metformin.
 
B. Metformin treatment group.

DEPENDENT VARIABLE	CONCEPTUAL DEFINITION	OPERATIONAL DEFINITION	CLASIFICATION	MEASUREMENT LEVEL	INDICATOR
FUNCTION OF THE PANCREATIC BETA CELL	Pancreatic beta cell's ability to secrete enough Insulin to keep blood glucose levels at normal levels.	Value obtained by the CTOG, when applying the formula $(\Delta I_{0-30})/(\Delta G_{0-30})$, (ΔI_{0-30}) = difference in insulin value measured at 0 and 30 minutes. (ΔG_{0-30}) = difference in glucose value measured at 0 and 30 minutes.	Quantitative	Reason	Pmol/mmol,
HOMEOSTASIS OF GLUCOSE	Ability of therapeutic interventions to reverse glucose intolerance.	It shall be considered as YES when the fasting glucose level at 6 months after the intervention begins, either at 2 h during CTOG is <140mg/dL, and NO when glucose levels at 2h during CTOG are 140mg/dL.	Qualitative	Dichotomous Nominal	Yes No

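### The printed sample-size formula and inputs give 20 evaluable patients per group, not 14; power at 14 is about 66% against the stated 80%

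*Combined protocol and SAP*

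**What the plan says.** Under Material and Methods, Sample size, the protocol expects 75% of patients to improve on the combination and 30% on metformin alone. It then sets the design target: "so the study is designed to detect a minimum difference of 45% between study groups with a type I (alpha) error of 0.05", with power of 80%. It prints n = (Zα/2 + Zβ)² × p̄(1 − p̄)(r + 1) / (d² × r), with 7.9 for the squared sum of z-values, failure proportions 0.25 and 0.70, r = 1 and d = 0.45. The result is "n = 14 + 20% of losses = 17 patients per group". No intermediate step is shown and p̄ is not defined.

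The number that will be analysed depends on two other places. The Elimination list removes patients for intolerance, for missing more than 20% of appointments, or on this ground: "That they do not finalize the study and monitoring protocol". Statistic Analysis says: "Analysis by intent to be treated and analyzed by protocol shall be performed". It gives no rule for a missing 6-month outcome.

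**The concern.** This paragraph is the only quantitative justification of the trial's size, and its stated result does not follow from the formula printed with it. The plan treats 14 as the number left after losses, because the 20% is added on top of it. If 14 is too small for the stated power, the shortfall applies to exactly the number the plan expects to analyse. A non-significant result would then be read as coming from an 80%-powered trial when it did not.

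Two related weaknesses sit in the same paragraph. The calculation compares proportions, but the three outcomes it names (insulin resistance, beta cell function, cardiovascular function) are classed as quantitative in the variables table. They will be compared by Student t or, if not normal, "otherwise the Mann-whitney U test will be used; to compare qualitative variables" go to chi-square. The only dichotomous outcome in that table is glucose homeostasis, defined as "Ability of therapeutic interventions to reverse glucose intolerance", and it is not among the three. In addition, the metformin rate ("metformin use alone achieves this only by 30%(44.46") is cited to references 44 and 46. The protocol's own account of these, under Treatment of Prediabetes, reports diabetes incidence and risk reductions for the first ("the risk of DM2 was reduced by 58%, and with metformin by 31" percent) and describes the second as a rosiglitazone trial. Neither account gives a proportion improving on metformin.

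**Working it through.** **Inputs** (all from the Sample size paragraph): (Zα/2 + Zβ)² = 7.9; p1 = 0.25 and p2 = 0.70 failing to improve; r = 1; d = 0.45. One assumption: p̄ is the mean of p1 and p2, the usual meaning with equal groups, so p̄ = (0.25 + 0.70)/2 = 0.475.

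**Attempt to reproduce 14**

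- p̄(1 − p̄) = 0.475 × 0.525 = 0.2494.
- n = 7.9 × 0.2494 × 2 / 0.2025 = 19.46, so 20 per group. The unrounded constant 7.849 gives 19.33, also 20.
- The stated 14 is not reproduced. The step from 14 to 17 is: 14 × 1.2 = 16.8, rounded up.

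**Could another p̄ give 14?** Between 0.25 and 0.70, p̄(1 − p̄) is smallest at 0.25, where it is 0.1875. The formula then gives 7.9 × 0.1875 × 2 / 0.2025 = 14.63, which rounds up to 15. Exactly 14 needs p̄(1 − p̄) = 14 × 0.2025 / (7.9 × 2) = 0.179, that is p̄ of about 0.234, which lies outside the range. Using p1 alone and truncating 14.63 would give 14, but nothing in the document says this was done.

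**Could another method give 14?** Other calculations from the same proportions:

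- unpooled variance, two-sided: 15.5 (16);
- arcsine, two-sided: 17.95 (18);
- pooled, one-sided: 15.2;
- arcsine, one-sided: 14.1 (15).

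The nearest ones are one-sided or unpooled, which contradicts the printed Zα/2, the 7.9 or the p̄(1 − p̄) term.

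**Power for 75% versus 30% improved, two-sided 0.05.** Inverting the printed formula, power = Φ(d / √(2p̄(1 − p̄)/n) − 1.96). At n = 14 this is Φ(0.45/0.1887 − 1.96) = Φ(0.424) = 66.4%. The pooled-null normal approximation uses the pooled variance under the null and the unpooled variance under the alternative. The exact figure enumerates all outcomes of an uncorrected chi-square.

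| Per group | Printed formula | Pooled-null normal | Exact uncorrected chi-square |
|---|---|---|---|
| 14 | 66.4% | 68.3% | 66.0% |
| 17 | 74.8% | 77.3% | 79.9% |
| 20 | 81.3% | 84.1% | 82.3% |

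**Detectable difference.** Against 30% improved on metformin, 80% power needs a difference of 50–53 points at 14 per group (80–83% improving) and 45–48 points at 17. The plan assumes 45.

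**Quantitative outcomes.** For a two-sample Student t test at two-sided 0.05, 80% power requires a true difference of 1.10 SD at 14 per group and 0.99 SD at 17.

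**Inflating 20 for losses.** 20 × 1.2 = 24 by the protocol's own method; 20 / 0.8 = 25 if 20% of those randomised are lost.

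**The case against.** Four points can be made on the other side.

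- **Power depends on the test.** Statistic Analysis names chi-square without saying whether it is continuity-corrected. With Yates correction or Fisher's exact test, power is about 52% at 14, 68% at 17 and 71–73% at 20. An unpooled normal approximation gives 76% at 14 and 84% at 17. Exact power also moves in jumps: the uncorrected chi-square gives 73% at 13 per group and 66% at 14. And 20% off 17 leaves 13.6, so 13 is possible. This stands as a caution on precision, but none of these methods reaches 80% at 14.
- **An intention-to-treat analysis is planned.** If all 17 contribute outcomes, exact uncorrected chi-square power is 79.9%, essentially the target. That is true, but patients who do not finish are eliminated and no rule covers missing outcomes, so 17 analysed cannot be assumed.
- **p̄ is undefined and the formula's source cannot be seen here.** The mean is an assumption. It is not decisive, because no value between the two proportions gives 14.
- **The responder comparison is not the planned analysis of the three named outcomes, and no threshold for improvement is defined.** This also stands. Any corrected power for 75% versus 30% describes the protocol's own sizing scenario, so the detectable difference for the quantitative outcomes should be given beside it.

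**Conclusion.** The stated sample size contradicts the formula and inputs printed with it: 20 evaluable per group are required, and the plan says 14, a shortfall of 6. With 14 evaluable, power for the planned effect is about 66%, so the chance of missing it is about one in three rather than one in five. With all 17 analysed, power is 75–80% and that chance is one in four to one in five. These power figures assume the printed pooled formula, its normal-approximation counterpart or an uncorrected chi-square, and 75% versus 30% improved. The figure of 20 assumes only that p̄ is the mean of the two proportions. The error does not touch the type I error or the treatment estimates. It must be fixed because the 80% claim would govern how a null result is read.

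**What to change.** Keep 17 per group and correct the Sample size text, for example:

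> With 17 randomised and 14 evaluable per group after 20% losses, power is about 66% for 75% versus 30% improved (75–80% if all 17 have outcomes). The formula requires 20 evaluable per group for 80% power.

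In the same edit:

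- define p̄, show the calculation, and name the test the power refers to, including whether chi-square is continuity-corrected;
- state the detectable difference for the quantitative outcomes in the Student t case: about 1.10 SD at 14 per group and 0.99 SD at 17;
- give the source of the 30% metformin rate and define improvement.

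This costs wording and a less favourable stated power; enrolment and analysis do not change. Enlarging the trial is optional. If 80% is to be kept, 20 evaluable means randomising 24 per group (20 × 1.2) or 25 (20 / 0.8). That is 48 or 50 patients in total instead of 34.
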